7.1 Adverse and Serious Adverse Event Reporting

The research team will notify GIRB of all study AEs & SAEs in accordance with policy guidelines. An SAE will be followed until either resolved or stabilized.

8 PROTECTION OF HUMAN SUBJECTS

8.1 Informed Consent

The informed consent form will be submitted to the IRB for review and approval.

Before any procedures specified in this protocol are performed, a subject must:

- Be informed of all pertinent aspects of the study and all elements of informed consent.
- Be given time to ask questions and time to consider the decision to participate.
- Voluntarily agree to participate in the study.

- Sign and date an IRB-approved informed consent form.

8.2 Protection of Human Subjects Against Risks

All studies with identifiable data carry the risk of the potential loss of privacy.

We will address this issue in several ways. First, all PHI will be stored on a secure, password protected network to which only limited number of research staff will have access. For data analysis, all data will be de-identified to the extent possible. Any information made available to other investigators will be in a HIPAA compliant format. PHI taken from the medical record will include name, medical record number, address, date of birth, date and type of surgery, appointment attendance, gender, race/ethnicity, weight, height, medications and medical conditions.

We believe that this study poses a low risk to participants; however, should any participant express significant psychiatric distress in group, including but not limited to suicidal or homicidal thoughts, the group leader (a clinical psychology resident) will assess the participant immediately after group and consult with the study PIs ([name] or [name]). The group leader and study PI(s) will refer the participant for further treatment as appropriate. The group leader may also ask disruptive participants to leave group at any time.

Should a participant report post-operative complications following bariatric surgery, the patient will be referred by group leaders or the study PI to the emergency room or to the bariatric surgery clinic, as appropriate.

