A member of the research team will remind the participants that randomize to the Intervention Group the day before each session either via phone or email (if participant chooses email communication they will provide the study team with their email address).

Should any participant express significant psychiatric distress in group, such as emotional reactions to weight loss or how relationships are affected, the group leader (a clinical psychology resident) will assess the participant immediately after group and consult with the study PIs ([name] or [name]). The group leader and study PI(s) will refer the participant for further treatment as appropriate. The group leader may also ask disruptive participants to leave group at any time.

Usual Care:

Participants randomized to usual care will complete surveys at postoperative clinic visits or if necessary, via mail. Upon study completion, patients randomized to usual care will be offered the 8 sessions provided to the BI group. This group will run after all study data have been collected.

Table 4. Compensation and Reimbursement

Behavioral Intervention Group	Compensation(Surveys) Reimbursement (Sessions)	Usual Care Group	Compensation (Surveys)
Baseline Surveys	\$50	Baseline Surveys	\$50
Session 1	\$15	N/A	N/A
Session 2	\$15	N/A	N/A
Session 3	\$15	N/A	N/A
Session 4	\$15	N/A	N/A
Session 5	\$15	N/A	N/A
Session 6	\$15	N/A	N/A
Session 7	\$15	N/A	N/A
Session 8	\$50	Final Surveys	\$50
TOTAL	\$205	TOTAL	\$100

Measures:

Surveys for Aims 1-2 will be administered to all participants at post op baseline (within two weeks of signing consent) and then at the completion of the 8 treatment session timeframe for both the BI and UC groups. Aim 3 measures of feasibility and satisfaction will be administered to BI participants only and at one time point, at study conclusion. Demographic, surgical and medical information will be collected from the EMR including weight (kg), height (cm), age at enrollment, sex, race/ethnicity, surgery type, insurance status, diagnoses and medication.

(Surveys are attached).

1. SF-36, Health-Related Quality of Life (HRQoL, primary outcome): As part of the Medical Outcomes Study (MOS), RAND developed the 36-Item Short Form Health Survey (SF-36). The SF-36 is a set of valid, reliable³⁴⁻³⁶, and easily administered QoL measures that have been used in obese populations^{37,38}.

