2. PHQ-9, Patient Health Questionnaire (depression): The PHQ-9 is a brief screening tool already integrated into GHS standard of care that screens for depression severity (sensitivity and specificity=88%). Scores of 5=mild depression, 10=moderate, and 15+=severe.
3. State-Trait Anxiety Inventory (STAI, anxiety): The STAI⁴⁰ is a 40-item assessment of anxiety symptoms and scored on a 4-point Likert scale. Internal consistency ranges from 0.86-0.95; test-retest reliability range 0.65-0.75 over a 2-month interval. It has demonstrated good construct and concurrent validity⁴⁰, and has been used in patients with obesity⁴¹.
4. Weight Efficacy Life-Style (WEL)⁴²: The Short form WEL is a 8-item measure that evaluates an individual's sense of self-efficacy in resisting the urge to eat in various situations. Internal consistency ranges from 0.70-0.90 and it has demonstrated sensitivity to change following weight loss interventions with obese populations.
5. The Paffenbarger Physical Activity Questionnaire (PPAQ)⁴³: The PPAQ is an 8-item, self-administered questionnaire designed to measure participation in leisure time. Respondents report the number of city blocks they walk and flights of stairs they climb on a typical day, as well as to list the frequency and duration of any sports or recreational activities they participated in over the past year. From these questions, a physical activity index (PAI) is computed, providing an estimate of energy expenditure. The PPAQ is used in bariatric surgery research⁴⁴.
6. Loss of Control Over Eating Scale-brief⁴⁵: The 7-item version of the LOCES is a brief measure of the experience of loss of control over eating over the past 28 days and is

[figure not shown]
scored on a 5-point Likert scale. The brief version of the full 24-item measure has demonstrated high internal consistency (0.93) and test-retest reliability ($r=0.82$) among non-clinical populations. The 7-item version is highly correlated with the 24-item version of the measure ($r=0.96$), which has also demonstrated good convergent and discriminant validity and was subjected to a more rigorous development and validation process than alternative measures.

7. Emotional Eating Scale (EES)⁴⁶. The EES is a 25-item scale that evaluates an individual's urge to eat while experiencing a range of emotions. The measure has demonstrated good discriminate validity, test-retest reliability, and sensitivity to change following treatment for weight loss and/or binge eating.

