7 SAFETY MONITORING

This study will examine the effect of a psychological intervention in bariatric surgery patients compared to usual care controls. The proposed assessments are believed to pose minimal risk to participants. Group leaders will continually monitor for adverse events during the study duration, including worsening psychiatric distress and post-operative complications associated with bariatric surgery.

A subject's AEs and SAEs will be recorded and reported from the signing of the informed consent form until completion of study.

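### The written psychiatric-distress pathway starts only with distress expressed in group, so it cannot operate for usual care during data collection or for anyone at baseline, and no supplied step acts on a severe study PHQ-9

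*Combined protocol and SAP*

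**What the plan says.** The psychiatric-distress response appears twice. Section 6.5, in the text on the behavioral intervention (BI), begins "Should any participant express significant psychiatric distress in group, such as emotional reactions to weight loss or how relationships are affected". Section 8.2 begins "should any participant express significant psychiatric distress in group, including but not limited to suicidal or homicidal thoughts". In both, the group leader acts: the leader "will assess the participant immediately after group and consult with the study PIs", and referral follows as appropriate.

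Section 6.5 gives the surveys to both arms at baseline and at the end of the eight-session period. They include the PHQ-9, with bands "Scores of 5=mild depression, 10=moderate, and 15+=severe". Usual-care (UC) participants complete surveys at clinic visits, or by mail where needed, and are offered the sessions only once data collection has ended. Section 6.3 places baseline surveys before randomization and lets participants complete them at home. Sections 6.9.1 and 8.3 have research assistants enter the data and provide for secure storage.

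Other safety text is wider. Section 7 says "A subject's AEs and SAEs will be recorded and reported from the signing of the informed consent form until completion of study" and "Group leaders will continually monitor for adverse events during the study duration, including worsening psychiatric distress". Section 7.1 says "The research team will notify GIRB of all study AEs & SAEs in accordance with policy guidelines" and requires serious events to be followed to resolution or stabilisation. The last paragraph of section 8.2 reads "Should a participant report post-operative complications following bariatric surgery, the patient will be referred by group leaders or the study PI", with no condition that the report be made in group.

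**The concern.** The background in section 3 names mood fluctuation and suicidality among the changes that may follow surgery. The trial then asks every participant for a depression-severity score and defines its severe band. The written clinical response, however, depends on a participant saying something in a group session, and half the sample has no session while data are being collected. A participant whose distress shows only on a survey form could have that form entered and filed with no instruction for anyone to respond. What is at stake is participant safety. No claim about bias or power is made.

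**Working it through.** The check sets the trigger beside the schedule.

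| Situation | Group available? | Can the in-group trigger operate? |
|---|---|---|
| BI, during the session period | Yes | Yes, for what is expressed in session |
| Both arms, baseline survey | No; it precedes randomization (6.3) | No |
| UC, randomization to final survey | No; sessions come after data collection (6.5) | No |

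The wording covers any participant in both sections, but the in-group condition still governs it, so it does not extend the pathway to the last two rows.

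Next, does any other supplied text fill those rows?

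- **Recording and reporting of adverse events (7, 7.1).** These cover both arms from consent, and serious events are followed up. They apply once an event is recognised. They set no PHQ-9 criterion and give no one the task of reading the form.
- **Monitoring by group leaders (7).** It spans the study, but UC participants have no group or group leader during data collection.
- **Data handling (6.9.1, 8.3).** Entry and storage are described; scoring on receipt and alerts are not.
- **Complications referral (8.2).** It has no in-group condition and can go through a PI, but it concerns postoperative complications. It shows that wider wording is workable.

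**Counts**, with about 80 participants and 40 per arm (6.1, 6.2.1):

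- PHQ-9 forms: 80 × 2 = 160. This is a ceiling, since enrolment is approximate and attrition is possible.
- Forms completed when the participant has no group: 80 at baseline + 40 UC final = 120 of 160, also a ceiling.

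**Context.** Table 1 in section 5 gives 1,005/3,695 = 0.272, which reproduces its 27.20% with a depression diagnosis before surgery. Section 6.2.3 does not exclude these patients.

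**Workload of a fix.** The documents give no rate for totals of 15 or more. Assuming 1% to 10% of forms, alerts number 0.01 × 160 = 1.6 to 0.10 × 160 = 16, or about 2 to 16 over the study. These are forms, not people, since one person can score high twice. Alerts raised for suicidal thoughts at a lower total would be extra.

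**The case against.** The strongest objection is that this is an absence, and the documents supplied cannot prove it. A PHQ-9 alert rule could sit in the attached surveys, telephone script or session outline, in the consent form, or in the IRB's policy guidelines, none of which was available. That stands. It limits the claim to the supplied text and means that the right correction may be only a citation.

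The second objection is that real protection exists. Adverse events are captured in both arms from consent and serious ones are followed. UC surveys are normally completed at clinic visits. The PHQ-9 is part of routine care in this health system, and candidates were cleared by psychology before surgery. The protocol rates the assessments as minimal risk. This narrows the gap without closing it. Surveys may be mailed or taken home, and nothing says that study scores reach the chart. Psychology clearance comes about 4 to 6 weeks before surgery, while enrolment is open up to 18 months after it.

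A reader might infer that UC participants have no safety coverage. The documents do not support that: sections 7 and 7.1 cover them. A reader might also multiply 27.2% by 80 and treat the result, about 22, as the expected number of severe scores. That is unsupported too, because it is a preoperative diagnosis rate and not a rate of postoperative totals of 15 or more.

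**Conclusion.** The point holds for the supplied text. Followed as written, the psychiatric-distress pathway cannot operate for about 40 UC participants during data collection or for any of the approximately 80 participants at baseline. No supplied step has anyone read or act on a study PHQ-9 in the band that the protocol itself calls severe. The existing protections are partial because none assigns that task.

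The extent is at most 120 of 160 forms completed when the participant has no group. The size of any harm is unknown and none is claimed; the 27.2% figure is context only. The documents do not show that the trial as a whole lacks an alert rule, because the attachments were not seen. Confidence is therefore medium. The change is worth making because it is cheap and concerns safety.

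**What to change.** In sections 6.5 and 8.2, change the trigger to distress expressed in group, at any study contact, or on a study survey, in both arms from consent. Then:

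- The research assistant totals each PHQ-9 on the day it is received, whether in clinic or by mail.
- Any total of 15 or more goes to a study PI the same working day. So does any response or comment indicating suicidal or self-harm thoughts, whatever the total, because a cut-off on the total need not catch these.
- The PI contacts the participant within a stated time, for example one working day, and refers as appropriate.
- Alerts and referrals are logged by arm.

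If an attachment already contains such a rule, cite it in section 8.2 instead.

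The cost is a short amendment, a little time from staff who already enter the forms, and PI time for roughly 2 to 16 severe-score contacts under the assumed 1% to 10%, plus any alerts for suicidal thoughts at lower totals. Some UC participants may be referred because of the survey. That could narrow the between-arm contrast in mood by an unknown amount; the by-arm log makes it visible.
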